6.3 Study Procedures

The expected flow of participants through the study is depicted in Figure 1.

[figure not shown]

Figure 1. Study Design Schematic

Community Intervention Group/Arm

For the intervention arm, community navigators will work with local businesses (barber shops, nail/hair salons, restaurants, etc.) to identify and screen eligible community members within the South Shore community area. In an effort to increase screening among the LGBTQ community, navigators will work with local entertainment venues to post the study flyer in order to provide information to patrons, and identify eligible participants for screening. The navigator will engage with each potential participant using the attached script. If the participant is interested, the navigator will review the study information sheet and ask the participant to provide written consent to participate. Once the participant agrees to participate, the navigator will collect contact information from the participant (see Participant Information Form), and provide the participant with a FIT, a short survey to complete and return with their FIT, and a postage paid envelope addressed for delivery to the UICC. The participant will also have the option to return the FIT at the barber or hair salon using a drop box. If the FIT is not returned within two weeks, the navigator will call the participant to remind them to return the FIT.

FITs will be returned via mail directly to the UICC, where they will be processed following the manufacturer's guidelines. Navigators will call back each participant to let them know about the results of their FIT using the attached script. If a participant screens positive, the participant will be informed by the navigator, who will direct the participant to the MSHC- South Shore Clinic, and connect the participant to the MSHC- South Shore clinical patient navigator. We will track the time between FIT dispensing and return, and the time between FIT processing and participant agreement to engage in diagnostic testing with the clinical navigator at MSHC as indicated (for those that screen positive). Once the FIT is returned, participation in the study will end. However, for those that have a positive/abnormal FIT, the community navigator will refer the person to MSHC for clinical follow-up. This is not part of the research, but to ensure a continuum of care among those that screen positive. The clinical navigator will follow the standard clinical flow and standard clinical care practices used at the MSHC- South Shore Clinic to schedule the participant for a diagnostic test, and any further procedures or treatments necessary. This will include, but is not limited to, helping the participant enroll in a health insurance program if the participant is uninsured, and/or obtaining a voucher to pay for the diagnostic/further screening examinations and tests. For CRC screening, we have partnered with administrative and clinical staff at the MSHC- South Shore clinic in the South Shore community area to facilitate this transition when needed.

Standard of Care Comparison Group/Control Arm

For the standard of care control arm, the lay patient navigator at Mile Square Englewood Health Center will provide deidentified aggregate data from the Mile Square Englewood patients that are approached following standard practice utilizing clinic schedules, walk-ins, etc. to identify potentially eligible participants for CRC screening during the intervention period. This aggregate data will include the number approached, the number eligible, the number that take and return the FIT kit, and the number of FITs returned. Among those that return the FIT, aggregate data will be provided detailing the

proportion of positive FITs, the proportion of positive FIT participants who return for diagnostic services, and the proportion of detected cancer.

For project evaluation purposes and to compare to the intervention arm, the deidentified aggregate data will include the number of participants who receive the FIT, return the FIT, screen positive, have a positive diagnostic, and receive a diagnosis. We will track the time between FIT dispensing and return, and the time between FIT processing and participant engagement in diagnostic testing as indicated (for those that screen positive).

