7.1 Expected Risks/Benefits

Potential Risks:

- Participants who engage in colorectal cancer screening by completing and returning the FIT may require diagnostic testing to evaluate if they have colorectal cancer. Some of the participants identified for diagnostic testing may or may not have colorectal cancer. Engaging in subsequent diagnostic testing and/or receiving a cancer diagnosis may cause these participants to feel psychological discomfort. All diagnostic and subsequent testing (as necessary) will be conducted within the MSHC system under standard of care, which has resources and trained staff to answer questions that participants may have during this time.
- Breach of confidentiality is another risk to individuals. To minimize the loss of confidentiality, the PHI collected for the participants will be kept on a password-protected UICC secure server network. No published data or public reports will have any identifiable information.
- We do not foresee any other physical, psychological, social, or legal risks to subjects.

Potential Benefits to Subjects and Society:

- An individual may benefit from participation in this study by having an existing cancer identified and diagnosed and being navigated to a source of treatment.
- Friends and family members of individual participants may benefit from increased awareness about colorectal cancer and the recommendations for screening.
- The potential benefit to society is that this study could have important public health implications future community based screening programs of adults. The information learned from this evaluation may aid future intervention or prevention studies.

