9.1 Data Analysis

- Prior to any analyses, all data sources (tracking, demographic, and questionnaire) will be cleaned and linked using the participant unique study identifier. We will summarize the data using frequencies and percentages for categorical variables, and means and standard deviations for continuous variables.

Aim 1: To assess the feasibility and efficacy of conducting a community-based CRC screening intervention in increasing CRC screening rates. We aim to evaluate the feasibility and efficacy of conducting a community-based navigation program for colorectal cancer screening. In both arms of the study, we will examine the number of participants who were provided with health education about colorectal cancer, the number of FITs distributed, and the number of FITs returned. We will summarize the number of persons screened positive and negative, and determine the proportion of positive screening participants who are referred to clinical care overall, and at the Mile Square South Shore and Englewood sites through our community navigation program (intervention) and existing MSHC lay clinical navigation program. We will compare the FIT return rate and average return time at the South Shore and Englewood sites to determine if the rates and times are similar. We will also determine return rates and times for participants who screen positive and are navigated to return the MSHC for diagnostic testing, and make comparisons across the intervention and control arms.

Aim 2: To evaluate individual-level knowledge related to CRC screening and risk factors. We aim to assess knowledge related to CRC screening and risk factors as measured by our short survey that participants will return with their FIT. We will summarize the frequency and percentage of respondents who have had a prior CRC screening, in addition to the frequency and percentage of respondents who select the correct answers on knowledge questions.

Aim 3: To characterize individual -level facilitators and barriers to engaging in CRC screening and related diagnostic tests and treatment when

applicable. We aim to evaluate facilitators and barriers people living in or near the South Shore communities experience related to CRC screening and related follow-up. We will summarize the respondent responses to survey questions about barriers and facilitators.

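### Section 6.3 ends the diagnostic follow-up interval at agreement in the intervention arm but at engagement under the control heading, and section 9.1 does not fix the date for its cross-arm comparison

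*Combined protocol and SAP*

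**What the plan says.** Section 6.3 describes follow-up of FIT-positive people separately for each arm.

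- **Intervention subsection:** the team will track "the time between FIT processing and participant agreement to engage in diagnostic testing with the clinical navigator at MSHC as indicated".
- **Control subsection:** the data are assembled "For project evaluation purposes and to compare to the intervention arm", and the team will track "the time between FIT processing and participant engagement in diagnostic testing as indicated (for those that screen positive").

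Under Aim 1, section 9.1 covers "return rates and times for participants who screen positive and are navigated to return the MSHC for diagnostic testing". For these quantities the plan is to "make comparisons across the intervention and control arms". It names neither a start date nor the recorded date that ends the interval. Section 12.1 adds no definition.

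Three other places bear on the point. The control data request, in sections 5.0 and 6.3, asks for the proportion of FIT-positive people who come back for diagnostic services. Section 8.1 lists the date of a completed diagnostic (colonoscopy) among the stored participant data. The intervention subsection of 6.3 also says that a person's participation finishes when the FIT comes back, and that clinical follow-up of a positive result falls outside the research.

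**The concern.** Agreeing to be tested comes before being tested. A clock stopped at agreement in one arm and at testing in the other compares an earlier event with a later one, so a shorter time in the intervention arm could come from the definition alone. A reader of the results could not tell this apart from a real effect of community navigation.

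The interval left out also matters in its own right. After agreement, the clinical navigator still has "to schedule the participant for a diagnostic test, and any further procedures or treatments necessary". Section 6.3 adds insurance enrolment or a voucher for some people, and section 5.0 adds registration as a patient. Those steps are part of getting a FIT-positive person to a test.

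The control data arrive as deidentified aggregates. If Englewood supplies times on a different event, the study team may have no individual dates from which to correct them.

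**Working it through.** The documents give no time, lag, FIT positivity or expected number of FIT-positive people, so there is no stated figure to reproduce. The check sets the texts side by side and then works out the direction algebraically.

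**Step 1. Definitions side by side.**

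| Place | Start | Stop |
|---|---|---|
| 6.3, intervention | FIT processing | agreement to engage in testing |
| 6.3, control | FIT processing | engagement in testing |
| 9.1, Aim 1 | not stated | a return to MSHC for testing; date not specified |
| 8.1, stored data | not applicable | diagnostic completed |

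The start is the same in both arms and the stop differs. The other tracked interval, from FIT dispensing to return, is worded identically in the two subsections of 6.3.

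**Step 2. What engagement means.** The protocol does not define it.

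- Section 7.1 supports reading it as doing the test: "Participants who engage in colorectal cancer screening by completing and returning the FIT may require diagnostic testing", and "Engaging in subsequent diagnostic testing and/or receiving a cancer diagnosis may cause these participants to feel psychological discomfort". The intervention wording, agreement *to engage*, also makes engagement the later event.
- Section 11.0 points the other way. It uses the word for FIT-positive people's dealings with the health centre, which is looser than having a test.

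**Step 3. Direction.** Let A be the time from FIT processing to agreement and L ≥ 0 the time from agreement to the test. Assume identical care in both arms, the 6.3 intervals compared as written, and engagement read as attending the test.

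- *Everyone who agrees is tested.* Intervention records mean(A) and control records mean(A + L). Intervention minus control = mean(A) − mean(A) − mean(L) = −mean(L). Any positive mean lag favours the intervention, and a lag of zero gives no bias.
- *Only some who agree are tested.* The two averages then cover different people: difference = mean(A, all who agree) − mean(A, tested) − mean(L, tested). Let p be the proportion of agreers who are tested. Then mean(A, all who agree) = p × mean(A, tested) + (1 − p) × mean(A, untested), so the difference is (1 − p) × [mean(A, untested) − mean(A, tested)] − mean(L, tested). If people who agree but are never tested were slower to agree, the first term is positive. It can then shrink the false advantage, and it reverses the sign if it exceeds mean(L, tested).

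No value of A, L or p is in the documents, so none is inserted.

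**Step 4. What is not touched.** The FIT return rate and the dispensing-to-return time do not use either stop event. The effect of this mismatch on them is zero.

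**The case against.** The strongest reply is that section 9.1 already points to the right kind of event. It speaks of a return to MSHC for diagnostic testing, which is close to the control request for the proportion who return for diagnostic services. Section 8.1 stores a completed-diagnostic date for participants, and nothing in 9.1 says that time to agreement will be the quantity compared. This stands in part: it would be wrong to infer that 9.1 is silent on the event. But a return could be a clinic visit, a meeting with the navigator or a completed test, and 9.1 does not choose among them or set aside the intervention definition in 6.3.

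A second reply is that this is loose drafting of one intended measure. The control sentence names no arm, and section 11.0 uses engagement for contact with the health centre. On that reading the gap between the two events may be small or nil. This is possible, but no text says so. The sentence sits under the control heading, directly after the description of the control data. If it applied to both arms, the intervention arm would have two different definitions, which would still need reconciling.

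A reader might also infer that the comparison is bound to favour the intervention. The documents do not support that. It requires the 6.3 intervals to be the ones compared and engagement to mean attending the test, and even then the sign can change if some agreers are never tested.

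Finally, this is a secondary comparison with no test or threshold attached. That is true, and it limits the weight of the point.

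**Conclusion.** The wording mismatch is certain: section 6.3 gives the two arms different stop events, and section 9.1 plans a cross-arm comparison without fixing the date. The resulting bias is conditional, and confidence in it is moderate. It rests on the 6.3 intervals being compared as written and on engagement meaning attendance at the test. Under those conditions, and if everyone who agrees is tested, the intervention arm would look faster by the mean agreement-to-test lag. The size is unknown, because the documents contain nothing from which to estimate it.

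A reader might extend this to the study's main result. That does not follow: the FIT return rate, which section 3.0 sets as the outcome of the arm comparison, does not depend on either stop event. The point concerns one secondary Aim 1 comparison among FIT-positive people, and it is worth correcting before the Englewood data are requested.

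**What to change.** 1. In both subsections of 6.3, use one start (FIT processing) and one stop event for FIT-positive people. Completion of the diagnostic test is a natural choice, because section 8.1 already lists its date as stored for participants.
2. Name the same start and stop in section 9.1. For each arm, report the proportion of all FIT-positive people who reach the event beside the time to it, with the number of people behind each average. A common pre-stated time window is optional; the mismatch itself does not require one.
3. Name the stop event in the Englewood aggregate data request. If Englewood cannot supply the matching event, make no cross-arm comparison of diagnostic time. The FIT return-rate and return-time comparisons can stay.
4. Keep time to agreement only as an intervention-arm process measure.
5. Reconcile the revised text with the statements in 6.3 that participation finishes at FIT return and that follow-up is outside the research, since 9.1 analyses what happens afterwards.

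**Cost:** wording changes in 6.3 and 9.1, a more specific data request, and a decision on how follow-up data sit within the research. Intervention follow-up times will look longer than time to agreement, and this one comparison may be lost.

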7.1 Expected Risks/Benefits

Potential Risks:

- Participants who engage in colorectal cancer screening by completing and returning the FIT may require diagnostic testing to evaluate if they have colorectal cancer. Some of the participants identified for diagnostic testing may or may not have colorectal cancer. Engaging in subsequent diagnostic testing and/or receiving a cancer diagnosis may cause these participants to feel psychological discomfort. All diagnostic and subsequent testing (as necessary) will be conducted within the MSHC system under standard of care, which has resources and trained staff to answer questions that participants may have during this time.
- Breach of confidentiality is another risk to individuals. To minimize the loss of confidentiality, the PHI collected for the participants will be kept on a password-protected UICC secure server network. No published data or public reports will have any identifiable information.
- We do not foresee any other physical, psychological, social, or legal risks to subjects.

Potential Benefits to Subjects and Society:

- An individual may benefit from participation in this study by having an existing cancer identified and diagnosed and being navigated to a source of treatment.
- Friends and family members of individual participants may benefit from increased awareness about colorectal cancer and the recommendations for screening.
- The potential benefit to society is that this study could have important public health implications future community based screening programs of adults. The information learned from this evaluation may aid future intervention or prevention studies.

8.1 Data Collection and Management Procedures

- Navigators will collect participant contact information for tracking and follow-up using REDCap.
- Survey data will be collected via a paper survey, which will be entered into REDCap. Following data entry, paper copies will be destroyed.
- All participant Protected Health Information (PHI), including contact

information, and full street address, unique participant ID numbers, demographic, the date a FIT was returned or diagnostic completed [colonoscopy]), navigation and follow-up data is stored on the University of UICC's password-protected secure server (K drive) in an encrypted Excel data entry workbook. Only the Principal Investigator (PI), Co-Investigators (Co-I), and key research personnel have access to the password-protected data entry workbook.

- Data will be harmonized and cleaned prior to analyses by the statistical team at the UICC and stored on the UICC secured server. All individual workstations at UIC that access data with PHI will be encrypted. PIs will have access to all data collected. Overall data management will be overseen by the PI and Research team.

9.1 Data Analysis

- Prior to any analyses, all data sources (tracking, demographic, and questionnaire) will be cleaned and linked using the participant unique study identifier. We will summarize the data using frequencies and percentages for categorical variables, and means and standard deviations for continuous variables.

Aim 1: To assess the feasibility and efficacy of conducting a community-based CRC screening intervention in increasing CRC screening rates. We aim to evaluate the feasibility and efficacy of conducting a community-based navigation program for colorectal cancer screening. In both arms of the study, we will examine the number of participants who were provided with health education about colorectal cancer, the number of FITs distributed, and the number of FITs returned. We will summarize the number of persons screened positive and negative, and determine the proportion of positive screening participants who are referred to clinical care overall, and at the Mile Square South Shore and Englewood sites through our community navigation program (intervention) and existing MSHC lay clinical navigation program. We will compare the FIT return rate and average return time at the South Shore and Englewood sites to determine if the rates and times are similar. We will also determine return rates and times for participants who screen positive and are navigated to return the MSHC for diagnostic testing, and make comparisons across the intervention and control arms.

Aim 2: To evaluate individual-level knowledge related to CRC screening and risk factors. We aim to assess knowledge related to CRC screening and risk factors as measured by our short survey that participants will return with their FIT. We will summarize the frequency and percentage of respondents who have had a prior CRC screening, in addition to the frequency and percentage of respondents who select the correct answers on knowledge questions.

Aim 3: To characterize individual -level facilitators and barriers to engaging in CRC screening and related diagnostic tests and treatment when

applicable. We aim to evaluate facilitators and barriers people living in or near the South Shore communities experience related to CRC screening and related follow-up. We will summarize the respondent responses to survey questions about barriers and facilitators.

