3.0 Objectives/Aims

We propose to address the multiple determinants of health that impact CRC screening in the South Shore community in the UI Cancer Center's catchment area by conducting a quasi-experimental intervention to test the effectiveness of FIT tests dispensed by community stakeholders (community-dispensed) versus FIT tests dispensed using standard of care procedures by a clinic (clinic-dispensed) on FIT test return rates. This

study will follow ACS guidelines for FIT testing, with the South Shore community area assigned to the intervention group (community-dispensed). CRC screening within the Mile Square Englewood Health Center, using standard of care, will serve as our control group to use for comparison (clinic-dispensed). The intervention will include a multifaceted approach to health education and community engagement focused on CRC led by a team of trusted health champions (community leaders, a barber, a hair salon, and community health workers) in the South Shore community area. We specifically propose to investigate the following three specific aims to be achieved over the three-year project period:

Aim 1: To assess the feasibility and efficacy of the community-based CRC screening intervention in increasing CRC screening rates;

Aim 2: To evaluate individual-level knowledge related to CRC screening and risk factors;

Aim 3: To characterize individual -level facilitators and barriers to engaging in CRC screening and related diagnostic tests and treatment when applicable.

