4.1 Eligibility

Community Intervention Group/Arm

Eligibility to participate in this community intervention will primarily be driven by location of residence and age, since screening CRC have established age criteria for screening initiation. A total of four community health navigators will be deployed in the South Shore community area. Each navigator will be trained to understand the eligibility criteria and determine subject eligibility. For those that consent to take the FIT kit and return it, the navigator will document the participants' eligibility in the appropriate REDCap participant information form (attached).

Standard of Care Comparison Group/Control Arm

Within the Mile Square Health Center system, lay navigators already work to do colorectal cancer screening in the Mile Square Health Center setting. It is standard of care for these navigators to engage patients in health education and awareness regarding the need for colorectal cancer screening. As such, each navigator is familiar with eligibility criteria for screening under standard of care. For the purposes of this study, we will use deidentified aggregate data from the CRC screening navigation program at the Mile Square Health Center in Englewood as a comparison group to evaluate the value of the community intervention relative to standard of care. As general practice, each navigator at MSHC keeps a running tally of the number of patients approached, deemed eligible, and who opt to participate in colorectal cancer screening during each day the navigator works in the health center setting.

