6.1 Study Design and Procedures

6.2 Dimensions of the RE-AIM framework

The overall aim of this study is to assess the feasibility and efficacy of the community-based CRC screening intervention in increasing CRC screening rates. We have designed this controlled trial in an effort to improve the quality of CRC screening that people receive and to assess whether or not implementing a community-based intervention where FIT tests are dispensed by community stakeholder will increase screening rates for CRC in specific community areas in

Chicago. If we find evidence supporting the efficacy of our intervention, that will demonstrate that community-based CRC screening interventions that actively involve community stakeholders in screening education and implementation may be a potential tool to improve health outcomes among the people that live in medically underserved communities. The RE-AIM framework will be used to evaluate both process and outcomes of the intervention program (Gaglio et al. 2013; Glasgow et al. 1999; Glasgow et al. 2019). The RE-AIM framework has proven utility in assessing program impact. Through the RE-AIM Framework we will be able to assess Reach, Effectiveness, Adoption, Implementation and Maintenance.

Data will be collected to evaluate our ability to “reach” targeted community members, hard to reach community members and the targeted number of participants. This is defined as the absolute number, proportion, and representativeness of individuals who are willing to participate in screening within our target community area. The clinical outcomes proposed through this project include improved screening of high risk populations for CRC screening and improved early detection of cancer through improved screening. To disseminate the findings to key stakeholders and community members, we will hold town hall forums to inform community members of findings from the project and produce infographics that clearly and succinctly communicate study findings.

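### Aim 1 asks whether screening rates rise, but 9.1 checks only whether FIT return is similar, with no effect estimate or interval and no between-arm comparison per eligible person

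*Combined protocol and SAP*

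**What the plan says.** The aim is directional. Section 3.0 gives Aim 1 as "To assess the feasibility and efficacy of the community-based CRC screening intervention in increasing CRC screening rates". Section 6.2 asks whether kits "dispensed by community stakeholder will increase screening rates for CRC in specific community areas in" Chicago, and looks ahead to a conclusion: "If we find evidence supporting the efficacy of our intervention, that will demonstrate that community-based CRC screening interventions".

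The outcome named for the test is narrower. Section 3.0 sets community-dispensed kits against those dispensed by "standard of care procedures by a clinic (clinic-dispensed) on FIT test return rates".

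Section 9.1 examines, in both arms, "the number of participants who were provided with health education about colorectal cancer, the number of FITs distributed, and the number of FITs returned". It then compares return rate and average return time at the "South Shore and Englewood sites to determine if the rates and times are similar". It also promises a between-arm comparison of diagnostic follow-up among FIT-positive people. The statistics it names are frequencies, percentages, means and standard deviations.

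Eligible people are to be counted in both arms. Under 4.1, each clinic navigator "keeps a running tally of the number of patients approached, deemed eligible, and who opt to participate in colorectal cancer screening", and 5.0 and 6.3 put the eligible count among the control aggregates. Section 5.0 has community navigators tally those approached, those eligible and those who decline. Section 6.2 defines reach to include the proportion willing to be screened, for the target community only.

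**The concern.** Two things do not fit the aim.

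- **Form of the comparison.** A question about an increase calls for an estimated difference with its uncertainty. Section 9.1 asks only whether the arms are similar, and neither 9.1 nor 12.1 names an effect measure or an interval. Two close percentages could then be called similar whether they rest on many control patients or few.
- **What is compared.** Return among kit recipients is conditional on accepting a kit, and people reach that point differently in the two arms: through community contact and written consent in one, through routine clinic practice in the other. If uptake differs, the return rate is not a stand-in for screening per eligible person.

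At stake is the conclusion foreseen in 6.2. A higher return rate could be reported as a higher screening rate when it is not one. Equally, similar return rates could hide a real gain in the number of eligible people screened.

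**Working it through.** **The plan's own figure.** Section 5.0 gives at least 600 community participants. It cannot be reproduced: the documents state no error rate, power, return rate, effect size, margin or control count. Section 12.1 says only that the size is expected to be sufficient. Apart from 600, every input below is assumed.

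**Step 1: how the measures relate.**

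returned / eligible = (distributed / eligible) × (returned / distributed), that is, screened = uptake × return.

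Section 9.1 compares only the last factor between arms.

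**Step 2: can the ranking change?**

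| Assumed case | Community | Clinic | Difference in return | Difference in screened per eligible |
|---|---|---|---|---|
| A | 40% × 70% = 28% | 70% × 50% = 35% | +20 points | −7 points |
| B | 60% × 50% = 30% | 30% × 50% = 15% | 0 points | +15 points |

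When the community return rate is the higher one, the ranking reverses if the ratio of community to clinic uptake falls below clinic return / community return. In case A that threshold is 0.50 / 0.70 = 0.71, and the uptake ratio is 0.40 / 0.70 = 0.57, so it reverses. In case B, return is identical while screening per eligible person doubles.

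**Step 3: how precise would a finding of similarity be?** Take 600 community kit recipients, n control recipients and the same observed return rate p in both arms:

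95% CI half-width = 1.96 × √[p(1 − p)(1/600 + 1/n)]

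| Control recipients n | p = 0.3 or 0.7 | p = 0.5 |
|---|---|---|
| 100 | 9.7 points | 10.6 points |
| 300 | 6.4 points | 6.9 points |
| 600 | 5.2 points | 5.7 points |
| 1200 | 4.5 points | 4.9 points |

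An observed difference of zero is thus compatible with true differences of up to about 10–11 points, or only about 4–5, depending on a control count that the documents do not give. These intervals cover sampling error only. With one non-randomised site per arm, they do not cover differences between the sites.

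**Step 4: are the counts available?** The counts for per-eligible rates are planned in both arms. For the return-rate denominator, the control lists in 5.0 and in the first control paragraph of 6.3 give approached, eligible, a combined take-and-return count, and returned; kits taken is not a separate item. The closing paragraph of 6.3 does list people who receive the FIT. The lists need to be brought into line.

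**The case against.** The strongest reply is that 3.0 itself names the FIT return rate as the tested effect and 9.1 compares exactly that. Return may be the plan's working measure of screening, and comparing two rates still shows direction. If the distributed and returned counts are reported, any reader can compute the difference and its interval. Section 12.1 presents the analyses as informing future interventions. This stands in part: for the return rate, what is missing is mainly analysis wording. It does not meet the conditioning problem, because no interval around return among recipients turns it into screening per eligible person. Nor does it cover return time, since the control lists promise no standard deviation.

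It is also fair that a per-eligible comparison has weaknesses of its own. Eligibility is established differently in the two settings. In the community, the participant form is described for consenters ("For those that consent to take the FIT kit and return it, the navigator will document" eligibility there), so for those who decline it rests on a tally. That is a reason to keep these rates descriptive and caveated.

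A reader might infer more than the documents support:

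- *That the denominator is unknown.* Kits distributed is the natural reading of 9.1 and of the closing paragraph of 6.3.
- *That uptake is ignored.* Section 6.2 plans a reach proportion, and 9.1 examines numbers educated and kits distributed in both arms. The gap is the missing between-arm comparison per eligible person.
- *That the community tally is seriously incomplete.* Section 5.0 does have a partner alert the navigator only about interested people at the barber shop or salon, so some who decline there may go uncounted. But 5.0 (community events), Table 2 and 6.3 also have navigators engaging potential participants directly. Nothing in the documents sizes any loss.
- *That an equivalence test is intended.* None is described.

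**Conclusion.** The point holds in this form. The comparison in 9.1 does not answer the question in Aim 1 and 6.2: it estimates no difference, gives no interval and, between arms, stops at return among kit recipients. That measure alone cannot support a statement that screening rates increased. The possible size is illustrated by case A (return +20 points, screened −7) and case B (return equal, screened 30% against 15%). All those rates are assumed, so they show that the measures can diverge, not that they will. The half-widths of about 4 to 11 points assume 600 community recipients, 100 to 1200 control recipients and return rates of 30% to 70%.

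The data remain usable and the repair is mainly to the text, so this should be changed but does not undermine the study as a feasibility project. A reader might infer that the planned analysis will give the wrong answer about efficacy; the documents contain no uptake or return figures from which to say so.

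**What to change.** In 9.1:

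1. Keep FITs returned / FITs distributed as the stated outcome. In place of the check for similarity, report the risk difference (intervention minus control) with a 95% CI, and the difference in mean return time, with a CI if the control site supplies n and SD. Describe this as a non-randomised, unadjusted comparison whose interval reflects sampling error only, not site differences.
2. Add FITs returned / eligible and FITs distributed / eligible in each arm as a descriptive companion comparison from the planned tallies. State that eligibility is established differently in the two settings and that some people who decline at partner contact (5.0) may not be tallied.
3. Do not conclude from the return rate alone that screening rates increased; otherwise word the conclusion as return among kit recipients.

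In 5.0 and 6.3:

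4. Reconcile the control-data lists so that the number who received a FIT is explicitly requested.

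The cost is analysis wording and one consolidated control-data request, plus n and SD for return time if the site can give them. The downside is that the per-eligible percentages will be lower than return among recipients and less comparable between settings, so they must always carry their caveat.
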